#### 6.14.6.7. Malignancies

Malignancies will be defined using PTs from the Malignant tumors SMQ and summarized separately for the 2 categories: Non-melanoma skin cancer (NMSC) and Malignancies excluding NMSC.

**Table KGAD.6.19. Summary Tables Related to Malignancies**

Analysis	Population
Summary of TEAE of malignancies within categories of NMSC and malignancy excluding NMSC	Modified Safety; Safety (sensitivity analysis)

Abbreviations: NMSC = non-melanoma skin cancer; TEAE = treatment-emergent adverse event.

#### 6.14.6.8. Atopic Dermatitis Exacerbation

Atopic dermatitis exacerbation will be defined using PTs specified in the Compound Level Safety Standards and summarized for Safety Population.

**Table KGAD.6.20. Summary Tables Related to Atopic Dermatitis Exacerbation**

Analysis	Population
Summary of TEAE of atopic dermatitis exacerbation	Modified Safety; Safety (sensitivity analysis)

Abbreviations: TEAE = treatment-emergent adverse event.

#### 6.14.6.9. Suicide/Self-Injury

The PTs from the suicide/self-injury SMQ [20000037] will be summarized.

**Table KGAD.6.21 Summary Tables Related to Suicidal Ideation and Behavior**

Analysis	Population
Summary of TEAE of suicide/self-injury	Modified Safety; Safety (sensitivity analysis)

Abbreviations: TEAE = treatment-emergent adverse event.

## 6.15. Subgroup Analyses

### 6.15.1. Efficacy Subgroup Analyses

Subgroup analyses will be conducted for the primary endpoints IGA 0,1 and EASI-75 at Week 16 in the mITT Population using MCMC-MI approach as in primary analysis (Section 6.4.1). A logistic regression analysis with treatment, subgroup, and treatment-by-subgroup interaction as factors will be used. The treatment-by-subgroup interaction will be tested using the Firth correction (Firth 1993) at the 10% significance level. Treatment group differences will be evaluated within each subgroup using the chi-square test, regardless of whether the interaction is statistically significant. If any group within the subgroup (for example, yes, no) is <10% of the total population, only descriptive statistics will be provided for that subgroup (that is, no inferential testing).

Forest plots may be created to illustrate the treatment differences with 95% CIs between each of the lebrikizumab treatment groups and placebo group, by each subgroup category.

The following subgroups will be analyzed:

- Age group (12<18, ≥18)
- Age group (Adolescents (12<18), Adults ≥18 to < 65, ≥65 to < 75, ≥75)
- Sex (male, female)
- Race (American Indian or Alaska Native, Asian, Black or African American, Native Hawaiian or Other Pacific Islander, White, Multiple, Other, Not Reported)
- Ethnicity (Hispanic or Latino, Not Hispanic or Latino, Not reported, Unknown) for US patients
- Region (as defined in Section 6.5)
- Weight category (<60 kg, ≥60 to <100 kg, ≥100 kg)

- BMI category Underweight ( $<18.5$  kg/m^2), Normal ( $\geq 18.5$  and  $<25$  kg/m^2), Overweight ( $\geq 25$  and  $<30$  kg/m^2), Obese ( $\geq 30$  and  $<40$  kg/m^2), Extreme obese ( $\geq 40$  kg/m^2)
- Duration since AD onset category (0 to  $<2$  years, 2 to  $<5$  years, 5 to  $<10$  years, 10 to  $<20$  years,  $\geq 20$  years)
- Baseline IGA 3 versus 4
- Baseline pruritus  $<4$  versus  $\geq 4$
- Prior use of systemic treatment (yes, no)

Some additional subgroup analyses may be added to meet regulatory requirement. The analysis of additional subgroups will not require an amendment to the SAP.

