### 6.1.2. General Considerations for Analyses

Treatment period starts after the first injection of study treatment at Baseline Visit (Day 1) and ends after patient completed Week 16 visit or the early termination visit (ETV) (between Day 1 and Week 16). For patients who are randomized but not dosed, the Double-Blinded Treatment Period starts on the date of randomization.

Baseline will be defined as the last available value before the first injection for efficacy and health outcome analyses. In most cases, this will be the measure recorded at Baseline Visit (Day 1). If the patient does not take any injection, the last available value on or prior to randomization date will be used. Change from baseline will be calculated as the visit value of interest minus the baseline value.

For Pruritus Numeric Rating Scale (NRS) and Sleep-Loss due to Pruritus collected via eDiary, the baseline period is the 7-day window prior to the first injection. A patient must have responses on at least 4 of 7 days to calculate a baseline weekly mean. If a patient has responses for 3 or fewer days, the baseline mean value will be considered missing. eDiary data for Pruritus NRS and Sleep-loss due to Pruritus are mapped to study visit per [Appendix 1](#).

For the safety analyses, the following baselines will be used. For safety analyses using a baseline period, the baseline period is defined as the time from Screening Visit to the date/time of the first injection in Treatment Period.

- Treatment-emergent adverse events (TEAEs): baseline will be all results recorded during the baseline period.
- Treatment-emergent abnormal laboratory and vital signs results: baseline will be all results recorded during the baseline period.
- Change from baseline to last observation or to each scheduled post baseline visit for laboratory and vital signs results: baseline will be the last scheduled non-missing assessment recorded during the baseline period.

The randomization to treatment groups is stratified by geographical region (US versus EU versus rest of world), age group (adolescent patients 12 to <18 years versus adults  $\geq 18$  years) and baseline disease severity (IGA 3 versus 4) as described in Section 5.3. The countries will be categorized into geographic regions for analysis (Section 6.3). Unless otherwise specified, the statistical analysis models for Treatment Period will adjust for geographic region, age group and baseline disease severity.

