### 6.3. Adjustments for Covariates

Unless otherwise specified, the statistical analysis models for the Treatment Period efficacy and health outcome analysis will include the following stratification factors for Baseline randomization: geographic region (US versus EU versus rest of world), age group (adolescent patients 12 to <18 versus adults  $\geq 18$  years) and baseline disease severity (IGA 3 versus 4).

Below are the country allocations within each geographic region.

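### SAP 6.15.1 leaves the randomisation factors out of the efficacy subgroup analyses without a stated reason: the tests stay valid, but chance imbalance in baseline IGA goes uncorrected in most subgroups

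*SAP*

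**What the plan says.** - **Subgroup model and test (SAP 6.15.1).** On the model: "A logistic regression analysis with treatment, subgroup, and treatment-by-subgroup interaction as factors will be used". On the interaction: "The treatment-by-subgroup interaction will be tested using the Firth correction (Firth 1993) at the 10% significance level". On the comparison inside each subgroup: "Treatment group differences will be evaluated within each subgroup using the chi-square test, regardless of whether the interaction is statistically significant". If any category of a subgroup variable "is <10% of the total population, only descriptive statistics will be provided for that subgroup".
- **Subgroup list (SAP 6.15.1).** Age group, region and baseline IGA are on the list. So are sex, race, ethnicity (US patients), weight, BMI, duration of AD, baseline pruritus and prior systemic treatment.
- **Default elsewhere.** SAP 6.1.2: "Unless otherwise specified, the statistical analysis models for Treatment Period will adjust for geographic region, age group and baseline disease severity". SAP 6.3 carries the same opening qualifier and says that the efficacy models "will include the following stratification factors for Baseline randomization", naming the same three factors. The overall IGA 0/1 and EASI-75 comparisons use a CMH test and a common risk difference, both adjusted for these factors.
- **Randomisation (SAP 5.3; Protocol 5.3).** Allocation is 2:1, stratified by region (3 levels), age group (2) and IGA 3 versus 4 (2).
- **Protocol 9.4.5** lists subgroups but names no subgroup model.

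**The concern.** Stratified randomisation balances severity between arms overall and, largely, within the region, age and IGA subgroups. It does not balance severity within women, within the heaviest patients, or within those with prior systemic treatment. If baseline IGA predicts response, as seems likely for an endpoint that requires a score of 0 or 1, a chance excess of IGA 4 patients in one arm of such a subgroup shifts the subgroup estimate, and the planned analysis does nothing to remove the shift. The subgroup odds ratios would also be unadjusted, while the overall odds ratio reported with them is adjusted. At stake is how supportive subgroup results read. The primary conclusion is not affected.

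**Working it through.** **Inputs from the documents.** 225 patients, 150:75; IGA 0/1 response 38% versus 13%; EASI-75 58% versus 20% (SAP 5.2); about 50 adolescents (Protocol 3.2); 10% floor for testing, 0.10 × 225 = 22.5, so about 23 patients (SAP 6.15.1).

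**Assumptions, not in the documents.** Share with IGA 4, q = 30% to 50%. Odds ratio of response for IGA 4 versus IGA 3 of 0.5, 0.33 or 0.2. No dropout applied.

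**1. The plan's own figure.** Power of the two-sided Fisher test at 150:75 is 98.4% for IGA 0/1 and above 99.9% for EASI-75. This agrees with the stated >95%. The plan gives no power or precision figure for subgroups.

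**2. Size of the chance imbalance.** In a subgroup not defined by a stratification factor, the between-arm difference in IGA 4 share has SD = √[q(1−q)(1/n₁ + 1/n₂)].

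**3. Standard error of the crude risk difference.** SE = √[0.38×0.62/n₁ + 0.13×0.87/n₂].

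| Subgroup (active:placebo) | Imbalance SD, q = 30% to 50% | SE of risk difference |
|---|---|---|
| 112 (75:37) | 9.2 to 10.0 points | 7.9 points |
| 75 (50:25) | 11.2 to 12.2 | 9.6 |
| 50 (33:17) | 13.7 to 14.9 | 11.7 |
| 23 (15:8) | 20.1 to 21.9 | 17.3 |

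In simulation, an imbalance of 10 points or more occurs in about 28-35% of subgroups of 112 and 45-55% of subgroups of 50.

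**4. What the imbalance does to the estimate.** Let d_T and d_C be the drop in response from IGA 3 to IGA 4 in each arm. At 2:1, a given imbalance is on average one third in the active arm and two thirds in placebo, so the risk difference moves by (d_T + 2d_C)/3 per unit of imbalance.

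- q = 30%, odds ratio 0.5: response is 43% versus 27% on active and 15% versus 8% on placebo. (0.16 + 2×0.07)/3 = 0.10, or 1.0 point per 10 points.
- q = 50%, odds ratio 0.2: 56% versus 20% and 21% versus 5%. (0.36 + 2×0.16)/3 = 0.227, or 2.3 points per 10.

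Simulation gives the same range, 1.0 to 2.3 points per 10.

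**5. Share of the sampling variance.** At n = 112 the lower case gives (0.10 × 9.2 / 7.9)² ≈ 1%, and the upper gives (0.227 × 10.0 / 7.9)² ≈ 8%. The share does not depend on subgroup size, because both SDs scale with 1/√n. So 8% is about the most that adjustment could remove under these assumptions.

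**6. What adjustment achieves in simulation** (crude chi-square against IGA-stratified CMH; 40,000 replicates).

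| Subgroup | Variance ratio, adjusted/crude | Power |
|---|---|---|
| 112 | 1.00 to 0.94 | about 83% to 82-86% |
| 75 | 1.01 to 0.94 | about 64% to 64-69% |
| 50 | 1.02 to 0.95 | about 48% to 46-50% |
| 23 | 1.07 to 0.99 | about 20% to 20-22% |

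With severity balanced by the randomisation, as for adolescents (33:17), adjustment changes nothing: SD 11.4 points and power 48% both ways. Type I error of the crude chi-square is 4.8-5.3%.

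**7. On the log-odds scale of the planned Firth model** (3,000 replicates, 225 patients, half-size subgroup, q = 40%, odds ratio 0.33). The crude log odds ratio implied by the plan is ln[(0.38/0.62)/(0.13/0.87)] = 1.41. The simulated unadjusted value is 1.40 (SE 0.558), and with baseline IGA added it is 1.47 (SE 0.568). The ratio of estimate to SE rises from 2.51 to 2.58, and power from 78% to 79%. The interaction SE rises from 0.798 to 0.812, and the interaction test at the 10% level rejects about 7% of the time either way.

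**The case against.** The sponsor has a good defence, and most of it stands.

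- **A reader might infer that the SAP contradicts itself.** It does not. The default in 6.1.2 and 6.3 gives way wherever another rule is specified, and 6.15.1 specifies one. Only the reason is missing.
- **A reader might infer that the subgroup results are biased.** They are not. The imbalance is random, the crude SE already includes it, and the crude test holds its level.
- **A reader might infer that the estimates are materially less precise.** The figures do not support that. The risk-difference variance falls by a few per cent at best, the log-odds SE rises slightly, and near the 10% floor stratification can cost precision.
- **A reader might infer that the subgroup analysis answers a different question from the primary one.** On the risk-difference scale, which is the population-level summary in SAP 6.2.1, crude and adjusted analyses target the same quantity. Only the odds ratio changes meaning (1.40 against 1.47 in logs above).
- **A reader might infer that the chi-square results cannot be pooled over imputations.** SAP 6.4.1 sends every specified analysis to PROC MIANALYZE, and the Appendix 3 transformation is written for general degrees of freedom. What is missing is detail, not a method.
- **Sparse data.** SAP 6.5 expects a logistic model with site and treatment-by-site terms not to converge. A subgroup of 15:8 has only 15×0.38 + 8×0.13 ≈ 7 expected responders, and the full stratification has 3×2×2 = 12 cells. This is a sound argument against stratified CMH in small subgroups. It does not count against main effects in a model fitted to all patients: there are at most four extra parameters, and 150×0.38 + 75×0.13 ≈ 67 expected responders to support them.

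**Conclusion.** Minor. SAP 6.15.1 takes a permitted exception to the adjustment default and gives no reason for it. The consequence is limited to subgroups not defined by region, age or IGA. There, severity imbalance of 10 points or more is common, but it moves the risk difference by only about 1-2 points per 10 points of imbalance, against an SE of 8-12 points in subgroups of 112 to 50. Expected gain from adjustment in subgroups of about 75 or more is roughly 0-4 power points and 0-8% lower risk-difference variance, where 8% is the ceiling from step 5 and the IGA-stratified simulation reached 6%. Near 23 patients there is none. The other benefit is consistency with the adjusted primary analysis.

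These sizes rest on the assumed IGA 4 share and prognostic strength; if baseline IGA predicts response only weakly, the gain disappears. The protection of the region, age and IGA subgroups could be slightly weaker than shown because the analysis population excludes one site after randomisation. The number excluded is not readable in the public text. The analyses are supportive and lie outside the multiplicity scheme in SAP 6.6.

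**What to change.** In SAP 6.15.1:

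1. Add baseline IGA, and region and age group, as main effects to the Firth logistic model fitted to the whole analysis population, leaving out whichever factor defines the subgroup. For ethnicity, which is analysed in US patients only, the region term drops out.
2. Take the interaction test and the within-subgroup treatment contrasts from that model, with standardised risk differences for the forest plots. The separate chi-square tests are then not needed.
3. Do not use stratified CMH in subgroups near the 10% floor.
4. If the unadjusted analysis is kept, state the reason in one sentence.

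The cost is SAP wording and up to four model terms (two for region, one each for age group and IGA), with a slightly larger SE on the log-odds scale. No new data are needed.

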### **6.15.2. Safety Subgroup Analyses**

Subgroup analysis for safety related endpoints will be performed within the context of the integrated safety analysis. Subgroup analyses may be added to meet regulatory requirement. The analysis of additional subgroups will not require an amendment to the SAP.

## **6.16. Protocol Deviations**

Protocol deviations will be identified throughout the study. Important protocol deviations (IPD) are defined as those deviations from the protocol likely to have a significant impact on the completeness, accuracy, and/or reliability of the study data or that may significantly affect a patient's rights, safety, or well-being.

Potential examples of IPDs include patients who violated the inclusion/exclusion criteria, used an interfering concomitant medication, significant non-compliance with study medication ( $<75\%$  of expected injections). Refer to a separate document called "KGAD Trial Issues Management Plan" for the IPDs with categorizations.

The number and percentage of patients having IPD(s) will be summarized within category and subcategory of deviation by treatment group for Treatment Period using the ITT Population.

A by-patient listing of IPDs for the ITT Population will be provided.

### **6.16.1. Impact of COVID-19**

Impact of pandemic (for example, COVID-19) on analyses may be addressed prior to study unblinding at Week 16 DBL, once the impact on study conducts are fully understood. In general, any missing assessments/visit window will be documented as protocol deviations. For patients who have missing assessments at Week 16 due to COVID-19, these patients may enter the escape arm. A summary or listing may be provided to summarize missing visits due to COVID-19.

Treatment discontinuation due to pandemic will be treated the same type of intercurrent event as treatment discontinuation due to reasons other than lack of efficacy. Strategies of how this type of intercurrent event will be handled are described in Section 6.2. Intermittent missing assessment due to pandemic will be treated the same as any other intermittent missing values. Details of how missing data will be handled are described in Section 6.4.

## 6.17. Interim Analyses and Data Monitoring

*Data Monitoring Committee/Data Safety Monitoring Board (DMC/DSMB):* The lebrizumab Phase 3 AD programs' DSMB is an independent expert advisory group commissioned and charged with the responsibility of evaluating cumulative safety at regular intervals, as well as on an ad hoc basis, as needed. The DSMB will consist of members external to Lilly and follow the rules defined in the DSMB charter, focusing on potential and identified risks for this molecule. Data Monitoring Committee membership will include, at a minimum, a physician with expertise in dermatology and a statistician. No member of the DSMB may have contact with study sites. This committee will make recommendations as to a) continue the clinical studies without modification; or b) continue the clinical studies with modifications; or c) terminate one or more of the clinical studies. Details outlining the roles and responsibilities of the DMC are documented in the "Dermira DRM06 DSMB Program Charter" and the planned analyses are outlined in the DMC analysis plan prior to the first unblinded assessment.

Access to the unblinded safety data will be limited to the DSMB. The study team will not have access to the unblinded data. Only the DSMB is authorized to evaluate unblinded data. The purpose of the DSMB is to advise Lilly regarding patient safety; however, the DSMB may request key efficacy data to put safety observations into context and to confirm a reasonable benefit/risk profile for ongoing patients in the study. Hence, there will be no alpha adjustment for these interim assessments.

*Week 16 Database lock (DBL):* An unblinded interim analysis will be performed at the time (that is, a cut-off date) the last patient completes Week 16 or the ETV from the study. This database lock will include all data collected by the cut-off date. Treatment assignment will be unblinded at the time of this interim lock.

*Final DBL:* A final DBL will occur after all patients have completed the safety follow-up period of the study, discontinued current study, or enrolled into the long-term extension study DRM06-AD07.

## 6.18. Annual Report Analyses

Based on regulatory requirements for the Development Safety Update Report (DSUR), reports will be produced (if not already available from the study CSR) for the reporting period covered by the DSUR.

## 6.19. Clinical Trial Registry Analyses

Additional analyses will be performed for the purpose of fulfilling the Clinical Trial Registry (CTR) requirements.

Analyses provided for the CTR requirements include the following:

Summary of AEs, provided as a dataset, will be converted to an XML file. Both serious adverse events (SAEs) and 'Other' AEs are summarized by treatment group and by MedDRA PT.

- An AE is considered 'Serious' whether or not it is a TEAE.

- An AE is considered in the ‘Other’ category if it is both a TEAE and is not serious. For each SAE and ‘Other’ AE, for each term and treatment group, the following are provided:
  - the number of participants at risk of an event,
  - the number of participants who experienced each event term, and
  - the number of events experienced.
- Consistent with [www.ClinicalTrials.gov](http://www.ClinicalTrials.gov) requirements, ‘Other’ AEs that occur in fewer than 5% of patients/subjects in every treatment group may not be included if a 5% threshold is chosen (5% is the minimum threshold).
- AE reporting is consistent with other document disclosures for example, the CSR, manuscripts, and so forth.

## 7. Unblinding Plan

Unblinding details are specified in a separated unblinding plan.

## 9. Appendices

## Appendix 1. Study Visit Mapping for Pruritus NRS and Sleep-loss Diary and PEOM

Pruritus NRS and sleep loss are collected as a daily diary; entries will be mapped to study week by the following:

Week	Start Day	End Day
Baseline	Date of First Injection a - 7	Date of First Injection - 1
Week 1	Max(Date of First Injection, Week 2 Office Visit Date - 14)	Week 2 Office Visit Date - 8
Week 2	Week 2 Office Visit Date - 7	Week 2 Office Visit Date - 1
Week 4	Week 4 Office Visit Date - 7	Week 4 Office Visit Date - 1
Week 6	Week 6 Office Visit Date - 7	Week 6 Office Visit Date - 1
Week 8	Week 8 Office Visit Date - 7	Week 8 Office Visit Date - 1
Week 10	Week 10 Office Visit Date - 7	Week 10 Office Visit Date - 1
Week 12	Week 12 Office Visit Date - 7	Week 12 Office Visit Date - 1
Week 14	Week 14 Office Visit Date - 7	Week 14 Office Visit Date - 1
Week 16	Week 16 Office Visit Date - 7	Week 16 Office Visit Date - 1

a If date of first injection is missing, the randomization date will be used.

If multiple assessments on a single day are present, use the first assessment. If an assessment could be mapped to different weeks, it will be mapped to the earlier week. During the Double-Blinded treatment period, prorated weekly average score will be calculated if at least 1 of the 7 days score is not missing. If the range of 7 days are all missing daily assessments, then the weekly result is missing.

Patient-Oriented Eczema Measure (POEM) scores are collected every week via eDiary; the visit-week mapping will follow the following rule: the last collected POEM data before or on the visit date would be used, the evaluation window is injection date - 7 to injection date -1 for baseline and assessment date - 7 to assessment date -1 for postbaseline. For example, if a patient gets an injection/assessment on the 14th, the scale completed in between the 13th and the 7th would be used. It is preferred not to use a POEM score, even if it is completed on the 15th or 16th, as those scores are now considered biased by the new drug administration. It is also preferred to not use data from 14th, because it is impossible to determine if the entry on 14th is before or after injection/assessment. To avoid bias, the 14th is excluded from evaluation window.

---

